The **long-term** goal of this research program is to determine the influence of IR on brain development in adolescents through the relationships between neurocognition and cerebral blood supply. The **primary goal of the current project** is to quantify fundamental neurocognitive and cerebrovascular function in relation to the severity of IR. **Our central hypothesis** is that as IR worsens: **a**) subtle but meaningful neurocognitive declines emerge; **b**) regional brain perfusion is reduced primarily in areas linked to learning and memory *despite* preserved resting global cerebral blood flow (CBF); **c**) acute insulin surges exacerbate regional hypoperfusion, and **d**) cognitive scores will be lower, mediated in part by insulin-stimulated hypoperfusion.

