##### 3.1.2. Preliminary Data

Pilot data indicate similar brain and hippocampal volumes between groups (2.93 vs 2.84 mm^3). Cognitive testing results did not differ significantly between groups. However, episodic memory, executive function, and attention, as well as total composite cognition scores were all quantitatively lower in adolescents with high IR. Notably, these smoldering decreases in cognition are directly correlated to HOMA-IR. Collectively, these data suggest brain structure remains intact at this stage, yet fundamental memory and attention measures are declining in relation to worsening insulin resistance.

#### 3.2. Aim 2

To test the hypothesis that adolescents with higher IR:

- a) exhibit intact resting global macrovascular CBF but reduced microvascular perfusion in key brain areas involved in cognition, memory, and learning
- b) will exhibit further perfusion reductions in response to an endogenous insulin surge in contrast to increased perfusion in healthy adolescents.

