## 8. STATISTICAL CONSIDERATIONS

Covariates for all analyses include sex, age, adiposity, aerobic fitness, and education unless noted otherwise.

The overarching statistical approach uses multiple regression to determine whether IR is inversely associated with outcome measures in Aims 1 and 2 and to assess mediation in Aim 3. Mean/summed outcomes (total cognition, total CBF or CP) will be predicted by HOMA-IR, for example. Not only is a composite measure calculated as a mean more reliable than the subdomain scores, but averaging multiple measures of a single construct yields a more powerful hypothesis test than using variables individually (40), under conditions we expect to hold here. This approach avoids inflation of Type I error rate as each hypothesis test examines the relationship among single variables or composites, not among multiple subdomain measures. If the test of the mean or composite score is significant, then there is no increased Type I error rate incurred in subsequent subdomain/regional tests (41).

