#### 8.3.1. Aim 2 Data Expression

For conceptual clarity, pilot data are expressed as CBF or CP. For statistics, the key dependent variable in Aim 2 is cerebrovascular conductance (CVC), where CVC is CBF or CP normalized to mean arterial pressure (i.e. blood pressure), where

$$\text{CVC} = \text{CBF}/\text{mean arterial pressure}$$

CVC is critical, as:

- 1) it normalizes CBF/CP for differences in mean arterial pressure (up to 15 mmHg across IR spectrum)
- 2) it accounts for mean arterial pressure changes *with* OGTT
- 3) changes in CVC ( $\Delta\text{CVC}$ ) have a predictable relationship *independent* of baseline differences, where  $+\Delta\text{CVC}$  indicates dilation and  $-\Delta\text{CVC}$  indicates constriction (24, 53)

$\text{CVC}_{\text{MACRO}}$  refers to macrocirculation (i.e. CBF) and  $\text{CVC}_{\text{MICRO}}$  to microcirculation (i.e. CP). While  $\text{CVC}_{\text{MACRO}}$  and  $\text{CVC}_{\text{MICRO}}$  are physiologically related, the two levels are conceptually independent. Testing both is crucial as preliminary data indicate resting CBF is normal, yet CP is lower as IR increases.

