#### 8.3.3. Aim 2B

The change in CVC ( $\Delta\text{CVC}$ ) will be predicted from HOMA-IR and the covariates, where

$$\Delta\text{CVC} = (\text{peak CVC during OGTT}) - (\text{resting CVC})$$

Pilot data indicate the average correlation between HOMA-IR and  $\Delta\text{CVC}_{\text{MICRO}}$  of  $-0.42$ , so a one-tailed test of the partial correlation will yield power of 0.80 with a sample size of **N=31**, with Type I error rate of 0.05. We plan to assess numerous regions of interest (ROIs) linked to executive functions and memory, including frontal, temporal, and parietal regions (e.g. middle, medial, and superior frontal gyri, anterior cingulate, hippocampus, middle and superior temporal gyri, posterior cingulate, precuneus), as well as ROIs *with less involvement* in memory or executive functions (e.g. precentral and postcentral gyri, occipital cortex).  $\Delta\text{CVC}_{\text{MICRO}}$  is only predicted from HOMA-IR within an ROI, not between, to limit the number of comparisons and therefore limit the false discovery rate.

For  $\Delta\text{CVC}_{\text{MACRO}}$ , up to 11 extra- and intra cranial arteries will be studied (basilar, 2 ACA, 2 MCA, 2 PCA, 2 vertebral, and 2 ICA; dependent on individual anatomy). Total CBF will be calculated, where

$$\text{CBF}_{\text{TOTAL}} = \text{CBF}_{\text{BASILAR}} + \text{CBF}_{\text{ICA-Right}} + \text{CBF}_{\text{ICA-Left}}$$

Pilot data indicate that the average correlation between HOMA-IR and MCA perfusion during OGTT is -0.796, so that a one-tailed test of the partial correlation will yield the power of 0.80 with a sample size N=6, with Type I error rate of 0.05. For all of Aim 2, if either total CVC test is significant (micro or macro), similar regression analyses will be performed to examine the mediating effects of  $\Delta$ CVC between HOMA-IR and individual ROI (micro) or artery (macro)  $\Delta$ CVC values.

#### 8.4. Aim 3

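### Aim 2b claims a fall in perfusion at high insulin resistance and a rise in healthy adolescents, but every test planned for it is a slope, which cannot show the sign of the response

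*Combined protocol and SAP*

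**What the plan says.** Section 3.2, item (b), states the hypothesis in two directions: adolescents with higher IR "will exhibit further perfusion reductions in response to an endogenous insulin surge in contrast to increased perfusion in healthy adolescents". Section 8.3.1 gives the sign of ΔCVC a physiological meaning: a positive value "indicates dilation and" a negative one constriction.

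Section 8 frames the statistical question as a graded one. The approach "uses multiple regression to determine whether IR is inversely associated with outcome measures in Aims 1 and 2". Section 8.3.3 follows this. ΔCVC "will be predicted from HOMA-IR and the covariates, where" ΔCVC is "peak CVC during OGTT" minus resting CVC. The microvascular test is powered from a pilot correlation of -0.42, "so a one-tailed test of the partial correlation will yield power of 0.80 with a sample size of" 31, and the macrovascular test from a pilot correlation of -0.796 for the middle cerebral artery (N = 6). If a total CVC test is significant, the follow-ups by region or artery are further regressions of the same type. Section 8.5 gives power of 0.95 for Aim 2B at N = 55.

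Section 8 plans no test or estimate of ΔCVC against zero and no fitted ΔCVC at any HOMA-IR value. It does not define high IR or healthy for analysis. Section 4.1.1 says that subjects are not recruited at set IR levels, so no group comparison fills the gap.

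**The concern.** The hypothesis concerns the sign of the response at each end of the IR range, while the test concerns the difference between the ends. A significant negative slope could be read as confirming Aim 2b when adolescents with high IR merely dilate less, or when those with low IR also constrict. Nothing in the planned analysis would separate these cases.

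At stake is the wording of the Aim 2b conclusion. So is the mediator's name in item (d) of the central hypothesis (Section 2.1), which presupposes hypoperfusion under insulin.

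**Working it through.** **Inputs from the documents.** r = -0.42, one-tailed α = 0.05, N = 31 (Section 8.3.3); N = 55 (Sections 4.1 and 8.5); six covariates, namely five in Section 8 plus intracranial volume in Section 8.3.2; four post-glucose scans of each type (Section 4.3.3.c).

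**Assumed.** The mean of ΔCVC at average HOMA-IR, called m, in SD units of ΔCVC, because the documents give neither a mean nor an SD; normally distributed HOMA-IR; covariates independent of HOMA-IR.

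**1. The plan's own figure.** One-tailed t-test with noncentrality |r|/√(1 - r²) × √N and N - 2 degrees of freedom.
- |r|/√(1 - r²) = 0.42/√0.8236 = 0.463.
- N = 31: noncentrality 0.463 × √31 = 2.58, power 0.808. N = 30 gives 0.796, so 31 is reproduced.
- N = 55: noncentrality 0.463 × √55 = 3.43, power 0.959, against the stated 0.95.

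The power statement is therefore right for the slope.

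**2. Why the slope is silent on sign.** The slope estimate is Σ(x - x̄)(y - ȳ)/Σ(x - x̄)². Adding a constant to every y changes neither this nor the residuals, so the t statistic is unchanged. The same holds with covariates and an intercept in the model. This is algebra and needs no assumption about m.

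**3. Illustration.** Simulated regressions with N = 55, r = -0.42 and six covariates. Fitted values are taken at the sample 10th and 90th percentiles of HOMA-IR, about ±1.28 SD, so the true means there are m ± 0.42 × 1.28 = m ± 0.54. The last column requires a significant slope, a 95% interval below zero at the high point and one above zero at the low point.

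| m (assumed) | True mean, low IR | True mean, high IR | Power of slope | Slope, fall and rise together |
|---|---|---|---|---|
| 0 | +0.54 | -0.54 | about 0.92 | about 0.50 |
| +0.2 | +0.74 | -0.34 | about 0.92 | about 0.33 |
| +0.42 | +0.96 | -0.12 | about 0.92 | about 0.08 |
| +0.8 | +1.34 | +0.26 | about 0.92 | below 0.01 |
| -0.8 | +(-0.26) | -1.34 | about 0.92 | below 0.01 |

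The simulated 0.92 is below 0.959 because HOMA-IR is random and its chance overlap with six covariates costs precision. Without covariates the simulation gives about 0.95. Deducting six degrees of freedom in the formula alone leaves 0.959.

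**4. The change measure.** If peak means the highest of the four post-glucose scans, then with no true change and exchangeable scans ΔCVC is positive unless the resting scan is the highest of five. That probability is 1 - 1/5 = 0.80. The expected value is 0.46 to 1.03 within-scan SD for between-scan correlations of 0.8 to 0 (assumed), or about +0.84 SD of ΔCVC throughout that range. A comparison of this ΔCVC with zero would lean towards a rise by construction. The plan does not say whether peak means the maximum or the largest absolute change; under the second meaning the bias differs.

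**The case against.** The strongest reply is that the plan mostly asks a graded question, and the slope answers it. Item (c) of the central hypothesis, that "acute insulin surges exacerbate regional hypoperfusion", is conditioned on IR worsening. Section 8 speaks of inverse association. Section 8.4 tests mediation by joint significance, and both paths (HOMA-IR to ΔCVC, ΔCVC to cognition) are slopes that need no fall below zero. All of this stands. A reader might infer that the mismatch undermines the central hypothesis as a whole or invalidates Aim 3B; the documents do not support that.

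Three further points also stand.
- The values of m are assumed. The pilot signs in Section 3.2.2 run in the direction claimed, though on two low-IR and three high-IR subjects (Section 3). Nothing shows that uniform dilation or constriction is likely.
- Section 8 contains no rule for wording conclusions, so it cannot be said that a sign claim would be made on the slope alone, only that nothing guards against it.
- Making slope, fall and rise a joint success criterion would be a poor remedy. Its power is about 0.50 at best, and with a maximum-based ΔCVC it would tend to reject the fall and confirm the rise. The slope is much less exposed, because a bias shared by all subjects goes into the intercept.

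The reply does not remove the explicit contrast of fall against rise in Section 3.2, or the reading of sign in Section 8.3.1.

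**Conclusion.** The concern holds in a limited form. The slope test is valid, and its stated power is reproduced. It supports a graded association and serves the Aim 3B paths. It cannot support the claim that perfusion falls at higher IR and rises in healthy adolescents, nor the mediator's label of insulin-stimulated hypoperfusion.

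That the slope ignores the overall level of response is certain. The figures of about 0.92 (slope) and at most about 0.50 (full sign pattern) rest on r = -0.42, the assumed m, normal HOMA-IR and independent covariates.

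Two stronger readings should be avoided. The study is not underpowered for its planned test. Nor will fitted values always settle the sign: at m = +0.8 the fitted mean at the 90th percentile is +0.26 with a 95% half-width of about 0.41, an interval of about -0.15 to +0.67, which would show neither a fall nor a rise.

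**What to change.** In Section 8.3.3:

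1. Keep the slope of ΔCVC on HOMA-IR as the powered test. In Section 8.5, say that the stated 0.95 applies to the slope only.
2. From the same regression model, report covariate-adjusted ΔCVC with 95% intervals at pre-specified low and high HOMA-IR values, for micro and macro. Justify the values in advance: sample percentiles depend on who enrols, and the pilot low-IR group itself averaged about 3.4 (Section 3), so a low percentile need not represent healthy.
3. Define peak. For the comparison with zero, fit the same model to a change measure that does not select the maximum, such as the mean of the post-OGTT scans minus rest, or a fixed time point minus rest.
4. State that a significant slope alone supports only a lower (less positive or more negative) response with higher IR. Claim a fall or a rise only where the interval at that HOMA-IR value supports the sign. Do not make slope, fall and rise together the success criterion.

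Alternatively, restate Aim 2b as a graded inverse association.

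The cost is a few lines of text, one further fit and two fitted values per outcome, with no new data, visits or subjects. The downside is that the sign claim becomes harder to support.

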**1. PROJECT SUMMARY**

One in five American adolescents are obese, and many of these patients exhibit some level of insulin resistance (IR). IR is associated with cerebrovascular disease, reduced memory, attention, and cognition, but how IR contributes to these in the course of adolescent brain development is unclear. The goal of this proposal is to investigate the extent and by which IR drives reductions in neurocognitive function and cerebral blood flow (CBF) in adolescents at elevated risk for poor brain and cerebrovascular health. We are testing the overall hypothesis that neurocognitive decline is linked to the severity of IR, as are reductions in brain perfusion, due to dysfunctional insulin signaling. We propose to study acute CBF control in healthy adolescents (12-18 years) across a range of IR (diabetes excluded) in collaboration with expert childhood neuropsychologists who lead a comprehensive cognitive testing protocol. Next, two complementary MRI methods (ASL and phase contrast MRI), along with a physiologic stressor to challenge CBF, will be used to test whether the impact of IR on brain macrovascular CBF and microvascular perfusion is regionally specific, with more negative effects in temporal and parietal lobes. These lobes are some of the initial brain areas to change in neurodegenerative diseases, and are involved in attention, memory, learning, and cognition. Finally, this study tests whether the degree of cognitive decline is linked to the CBF stress response and to severity of IR, and to what extent brain hypoperfusion mediates the IR-driven lower cognitive function. This study will provide the first comprehensive look at IR in adolescent brains, by utilizing extensive neuropsychological testing and state-of-the-art MR imaging, and drawing on interdisciplinary collaborations between developmental neuropsychologists, vascular physiologists, and pediatric endocrinologists. These studies are designed to uncover fundamental relationships between IR, neurocognitive function, and CBF in these blossoming adolescent brains. Exciting preliminary data support the aims—particularly uncovered by a physiologic insulin surge—signifying these findings will serve as a foundation for prospective, mechanistic studies to reduce the burden of IR and improve brain and cognitive health in this clinically important population.

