### 2.3. Innovation

Many youth-focused brain studies emphasize a sole aspect of brain structure, cognitive function, or CBF. A limitation of intriguing, but associative studies is that they assess effects of IR on resting measures in adolescence, obscuring insight into the daily impact of insulin on brain health (26, 37). These resting associations lack high resolution in terms of mechanistic insight, and thus add fuel to a classic chicken or egg question: Does vascular dysfunction or neural dysfunction dominate the *earliest* brain changes in adolescents with IR? To address several limitations, this proposal combines three unique areas of innovation. First, this proposal combines collaborative expertise in pediatric neuropsychology, pediatric endocrinology, and vascular physiology to address the complexities and subtleties of the preclinical disease process. A second innovation stems from combining two powerful, complementary brain-imaging approaches that quantify brain perfusion and identify the regions most impacted by IR. **Phase-Contrast Vastly-undersampled Isotropic Projection Reconstruction, (PC VIPR)** is a high-resolution, 4D flow approach used to quantify macroscopic CBF in *all* major extracranial and intracranial arteries. Arterial Spin Labeling (**ASL**) measures provide insight into microvascular cerebral perfusion allowing identification of focused brain regions impacted by IR. No single measure of flow or perfusion can comprehensively assess cerebrovascular function in health or IR; the combination of both MRI approaches will greatly enhance insight into CBF regulation in adolescence. Third, clinically relevant insulin surges acutely stress brain blood flow regulation, highlighting cerebrovascular dysfunction that is not apparent at rest. Indeed, we present novel pilot data indicating significant neurocognitive decline along with remarkable cerebrovascular dysfunction, both of which are related to the severity of IR. When combined, the technical and conceptual innovations in this proposal will deliver novel insight into the severity and regional impact of IR on brain health and cognition in adolescents.

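### The narrative sections make comparative claims about brain regions, but the analysis plans only within-region tests and no contrast between regions

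*Combined protocol and SAP*

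**What the plan says.** Four narrative places compare regions:

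- Section 1 (Project Summary) says the imaging will test whether the IR effect is "regionally specific, with more negative effects in temporal and parietal lobes".
- Section 2.1 (Synopsis) hypothesises that "regional brain perfusion is reduced primarily in areas linked to learning and memory".
- Section 2.3 (Innovation) says the two imaging approaches "quantify brain perfusion and identify the regions most impacted by IR".
- Section 3.2.2 (Aim 2 Preliminary Data) repeats the Innovation claim in its summary of what the combined MRI methods allow.

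The analysis is in Section 8. Section 8.3.3 names nine example ROIs linked to executive function and memory, in frontal, temporal and parietal regions. It names three more that are less involved "in memory or executive functions (e.g. precentral and postcentral gyri, occipital cortex"). It then states that ΔCVC_MICRO "is only predicted from HOMA-IR within an ROI, not between, to limit the number of comparisons and therefore limit the false discovery rate".

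Regional tests follow the total test: "For all of Aim 2, if either total CVC test is significant (micro or macro"), then "similar regression analyses will be performed to examine the mediating effects of" ΔCVC on individual ROI or artery values. Section 8 gives the general reason for testing composites first: "This approach avoids inflation of Type I error rate as each hypothesis test examines the relationship among single variables or composites".

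**The concern.** A claim that one region is affected more than another is a claim about a difference between slopes. A within-ROI regression estimates one slope against zero. Twelve such regressions give twelve answers to that question and none to the comparative one. The comparison ROIs are measured, but the plan never compares them with anything.

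If the plan is followed exactly, regional specificity could only be read from the pattern of significant and non-significant ROIs. That pattern varies by chance even when the effect is uniform, so a uniform effect could be reported as regional.

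The target set is also not settled. Section 1 names temporal and parietal lobes, Section 2.1 names learning and memory areas, and Section 8.3.3 adds frontal regions while placing the postcentral gyrus among the comparison ROIs. The grouping could therefore be chosen after the data are seen.

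**Working it through.** **1. The plan's own figures reproduce.** For a one-tailed test of a correlation, power is the upper tail of a noncentral t with N−2 degrees of freedom and noncentrality r√(N/(1−r²)).

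- Aim 2B micro, r = 0.42, N = 31: 0.42 × √(31/0.8236) = 2.577, critical t = 1.699, power 0.81. N = 30 gives just under 0.80, so N = 31 is confirmed.
- Aim 2A, r = 0.324, N = 55: noncentrality 2.540, critical t = 1.674, power 0.806 (stated 0.8).
- Aim 2B at N = 55: noncentrality 3.432, power 0.959 (stated 0.95).

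These are powers for one slope at a time. None is given for a difference between regions.

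**2. Two ROIs with the same true effect.** With N = 55, six covariates removed and inter-ROI correlation from 0.8 down to 0.3 (assumed), one ROI is significant and the other is not in 8–13% of simulated studies at r = −0.42, and in 17–33% at r = −0.324.

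**3. The twelve example ROIs, same true effect everywhere.**

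Inputs from the documents:
- Five general covariates (Section 8) plus intracranial volume (Section 8.3.2) make six, so 55 − 6 = 49 effective observations and 47 degrees of freedom.
- One-sided α = 0.05.
- r = −0.324 (resting pilot value) and r = −0.42 (glucose-load pilot value).

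Assumptions:
- Nine target and three comparison ROIs, as in the examples.
- r = −0.25 as a weaker case.
- Inter-ROI correlation either equal (0.3, 0.5, 0.7) or higher within a set than between sets (0.5/0.3, 0.7/0.5, 0.7/0.3, 0.8/0.5).
- Total CVC_MICRO is the ROI mean, and regional tests are read only if that total is significant.

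The plan gives no rule for reading specificity, so three are shown.

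| What is reported as regional, with no true difference | r = −0.25 to −0.324 | r = −0.42 |
|---|---|---|
| Larger share of target than comparison ROIs significant | 19–37% | 10–18% |
| At least half of target, under half of comparison | 7–19% | 3–5% |
| At least one target, no comparison | 2–13% | 0–2% |
| One contrast, raw units, ungated | about 5% | about 5% |

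If each ROI is z-scored and reliability is equal, the contrast errs 2–5%. Because the macro total can also open the gate, the loosest reading at r = −0.25 to −0.324 lies between the tabled rate and the ungated 24–42%.

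**4. Power of the contrast, ungated, at N = 55 (approximate).**

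| True r, target vs comparison | Equal correlation | Higher within-set correlation |
|---|---|---|
| −0.42 vs −0.20 | 0.90 to above 0.99 | 0.47–0.70 |
| −0.324 vs −0.20 | 0.45–0.79 | 0.21–0.31 |
| −0.42 vs −0.30 | 0.42–0.76 | 0.19–0.28 |
| −0.324 vs 0 | above 0.99 | 0.77–0.95 |

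Gating the contrast on the micro total cuts the last equal-correlation entry to 0.64–0.91.

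**5. Scale.** With equal true effects but unequal reliability (assumed 0.9 vs 0.6, or 0.8 vs 0.5), a z-scored contrast errs 11–28% and a raw-unit contrast 5%. The raw-unit contrast in turn reflects differing baseline levels.

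**6. The follow-up wording in Section 8.3.3.** CBF_TOTAL is the sum of the basilar and the two internal carotid flows. Those three arteries are also among the eleven individual outcomes (1 + 2 + 2 + 2 + 2 + 2). A mediation analysis with the total as mediator and one of its summands as outcome has the outcome inside the mediator. For ROIs the same problem arises only if total CVC_MICRO is built from them, which is not stated.

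**The case against.** The formal aim makes no between-region claim. Aim 2a in Section 3.2 speaks of reduced perfusion in key areas, which within-ROI tests can address. Section 1 says it will test, Section 2.1 states a hypothesis, and Sections 2.3 and 3.2.2 describe what the imaging can do. This stands: the gap lies between the narrative and the analysis section, and a reader who inferred that an aim, the sample size or a stated power is wrong would go beyond the documents.

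The harm is smallest where the quoted rule applies. That rule governs ΔCVC_MICRO, with pilot r = −0.42, and there only the loosest reading does worse than the contrast. The larger rates use the resting value or an assumed weaker one, and all need a reading rule that the plan does not contain. The −0.324 is given for resting CVC_MICRO and is used here as a per-ROI value. Rescaling for that leaves the loosest rate similar, at 20–33%. This also stands, and it limits the size of the point without removing it.

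Limiting comparisons is a legitimate aim, but it does not justify the omission. One composite contrast adds one test per condition to a dozen or more ROI tests, and Section 8 itself prefers composites for error control. The gate on the total addresses only whether there is any effect overall.

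A reader might also infer that the resting CVC_MACRO test in Section 8.3.2 will be taken as proof of intact flow. That section says only that a relation will be tested and is not expected. It does not say a non-significant result will be read that way, so this is not an error in the plan.

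**Conclusion.** The point holds as a mismatch between stated questions and planned analysis. The comparative statements in Sections 1, 2.1, 2.3 and 3.2.2 are left untested, because Section 8.3.3 excludes between-ROI prediction for ΔCVC_MICRO and nothing in Section 8 supplies a contrast at rest or after the glucose load. That follows from the text and needs no assumption.

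The size of the risk is less certain. It depends on ROI correlations, ROI counts and a reading rule, none of which the documents give. The loosest reading is clearly worse than a contrast across the range examined; at r = −0.42 the stricter readings are not.

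A reader might infer that a contrast would settle the regional question. The figures do not support that: power runs from roughly 0.2 to above 0.99, so the contrast may be inconclusive. The change is worth making, but no planned total-score test or sample size depends on it.

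**What to change.** Choose one of two routes.

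**(A) Test the claim.** Prespecify one contrast at rest and one for ΔCVC_MICRO: mean of target ROIs minus mean of comparison ROIs, regressed on HOMA-IR and the covariates, reported as an estimate with a confidence interval.

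- Do not gate it on the total CVC test.
- Fix one primary scale in advance, raw units or z-scores, and keep the other as sensitivity only.
- Fix the ROI list and grouping, and reconcile Sections 1, 2.1 and 8.3.3 on which regions are targets.
- State that a null contrast will not be read as absence of specificity.

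Cost: wording, two extra tests on data already collected, and uncertain power.

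**(B) Narrow the claim.** Remove the comparative wording from Sections 1, 2.1 and 2.3 and from the methods sentence in Section 3.2.2. Leave the pilot results in Sections 3.2.2 and 8.3.2 as they are. Report each ROI as an estimate with a confidence interval and no ranking. Cost: wording only.

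**Under either route,** replace the mediation follow-up in Section 8.3.3 with direct regression of each ROI or artery ΔCVC on HOMA-IR and the covariates. Reporting resting CVC_MACRO with a confidence interval is optional.

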#### 8.3.2. Aim 2A

Total CVC will be predicted from HOMA-IR and the covariates (intracranial volume is an additional covariate for CVC analyses). Resting CP data indicate reduced perfusion in several anterior brain regions. Pilot data yielded a correlation between HOMA-IR and resting  $\text{CVC}_{\text{MICRO}}$  of  $-0.324$ , such that a sample of size **N=55** will yield the power of 0.8 in a one-tailed test of the correlation, with Type I error rate of 0.05. In contrast, we will test, but do not expect, resting  $\text{CVC}_{\text{MACRO}}$  to be related to HOMA-IR, since resting  $\text{CVC}_{\text{MACRO}}$  is similar in low and high IR.

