Aim 3 tests the mediation effects of CVC on the relationship between HOMA-IR and the composite cognition scores assessed in Aim 1. Mediation will be assessed using the test of joint significance (23). The path between HOMA-IR and perfusion will have been examined in Aim 2. At rest (Aim 3A), mean  $CVC_{MICRO}$  and  $CVC_{MACRO}$  will be examined as the primary mediating variables. Pilot data indicate the correlation between resting  $CVC_{MICRO}$  and cognition is 0.37, so that a sample size of **N=41** would yield 0.8 power in a one-tailed test and Type I error rate of 0.05. During OGTT (Aim 3B), mean peak  $\Delta$ CVC will be the primary mediator variable. Pilot data indicate that the partial correlation between post-OGTT  $\Delta CVC_{MICRO}$  and the total cognitive score was 0.4, so that a directional test of this path requires a sample size of **N=34** to yield the power of 0.8 with Type I error rate of 0.05. A similar power is achieved for  $CVC_{MACRO}$ . If either test (rest or OGTT challenge) is significant, analyses will be performed to examine the mediating effects of CVC between HOMA-IR and individual cognitive ability domain scores.

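### As written, the 'either' gates in 8.3.3 and 8.4 let one family's or state's significant total open follow-up tests in another whose own total was not significant

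*Combined protocol and SAP*

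**What the plan says.** Section 8 gives the general argument on multiplicity: "If the test of the mean or composite score is significant, then there is no increased Type I error rate incurred" in the subdomain or regional tests that follow. Aim 1 (8.2) applies it directly, since one cognitive composite gates its own subdomains.

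Aim 2 has two levels, micro (ASL perfusion) and macro (artery flow), and two states, rest (2A) and change during OGTT (2B). The gate at the end of 8.3.3 reads "For all of Aim 2, if either total CVC test is significant (micro or macro), similar regression analyses will be performed". The follow-ups it names are individual ROI values (micro) and individual artery values (macro), expressed as change in CVC.

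Aim 3 (8.4) has a parallel gate: "If either test (rest or OGTT challenge) is significant, analyses will be performed" of mediation for the individual cognitive domains.

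Neither sentence limits the follow-ups to the level or state that passed. No adjustment is planned across the totals or within the follow-ups.

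**The concern.** A gatekeeping argument works when the gate is the composite of the family that is then examined. If every member of that family is null, its composite is falsely significant only 5% of the time, so false findings among the members stay near 5%. If another family's result opens the gate, that protection is lost and the members are simply tested side by side, unadjusted.

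Split results are foreseeable. Section 8.3.1 treats micro and macro as separate concepts. Section 8.3.2 powers resting micro at 0.8, but says of the macro total at rest "In contrast, we will test, but do not expect, resting" CVC to be related to HOMA-IR. So at rest the plan itself expects one total to pass and the other not to.

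What is at stake is the regional claim. The project summary and the central hypothesis say that the effect of IR is concentrated in particular brain areas. An ROI, artery or domain finding could be read as covered by Section 8 when its own family's total showed nothing.

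**Working it through.** **Inputs from the documents.** One-tailed tests at 0.05; N=55; r=-0.324 for resting micro (8.3.2); r=-0.796 for MCA perfusion during OGTT (8.3.3); 12 ROIs named as examples and up to 11 arteries (8.3.3); five general covariates (Section 8) plus intracranial volume for CVC (8.3.2), so six.

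**Assumptions.** Correlation within a family 0 to 0.9 and between families 0 to 0.6; the documents give neither. Each follow-up is a one-sided 0.05 regression test, like the totals. The composite is the family mean.

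**Step 1: reproduce the plan's figure.** For Aim 2A the plan says N=55 "will yield the power of 0.8 in a one-tailed test of the correlation, with Type I error rate of 0.05". Use the noncentral t with df = N-2 and ncp = |r|/√(1-r²) × √N.
- 0.324/√(1-0.105) = 0.342, and 0.342 × √55 = 2.54. Power is 0.806, and N=54 falls just short of 0.80, so N=55 is reproduced.
- The same formula returns the plan's N of 13, 31, 6, 41 and 34 for the other tests.

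**Step 2: how often the gate opens.**
- Resting micro, r=-0.324, six covariates: df = 47 and ncp = 0.342 × √49 = 2.40, giving power 0.76. The Fisher z version, with √(55-3-6), gives 0.74. The simulation below uses 0.74.
- Macro at the pilot r=-0.796: power is essentially 1 at N=55. At an assumed r=-0.4 it is 0.94, or 0.91 after six covariates.

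**Step 3: error in a fully null family.** The calculation can be checked by hand with independent members:
- 12 ROIs, gate always open: 1-0.95^12 = 0.46.
- 11 arteries: 1-0.95^11 = 0.431. The micro gate opens with probability 0.74. Otherwise only the family's own false gate counts (0.044). So 0.431 × 0.74 + 0.26 × 0.044 = 0.33.

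Simulation (400,000 replicates) over the correlation range gives:

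| Correlation within family | ROIs null, macro total almost surely significant | Arteries null, micro total real at r=-0.324 (between-family correlation 0 to 0.6) |
|---|---|---|
| 0 | 0.46 | 0.33 |
| 0.3 | 0.34 | 0.25 to 0.29 |
| 0.5 | 0.27 | 0.20 to 0.24 |
| 0.7 | 0.20 | 0.15 to 0.18 |
| 0.9 | 0.12 | 0.10 to 0.12 |

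With each family opened only by its own composite, the error is 0.044 to 0.051 throughout.

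**Step 4: sensitivity to the macro effect.** With macro power 0.91 instead of 1, taking the gates as independent, the ROI figures become 0.46 × 0.91 + 0.09 × 0.045 = 0.42, down to 0.12 × 0.91 + 0.09 × 0.05 = 0.11.

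**Step 5: everything null.** With the 'either' gate, the error in any one family is only 0.053 to 0.072. The problem arises when one total is real and the other null.

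No error rate was computed for Aim 3.

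**The case against.** **The Aim 2 sentence may be meant respectively.** It puts micro and macro in parentheses after the totals and again after ROI and artery. A reader could take it that micro opens ROIs and macro opens arteries, which agrees with Section 8. This is a fair reading, and if intended it removes the micro-macro crossing. But the text does not say so. Its scope, all of Aim 2, does not separate rest from OGTT, and the Aim 3 sentence has no such pairing.

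**The largest figures are not the plan's expected case.** The ROI column assumes a real macro effect and null micro. For the change during OGTT the plan expects micro to be related too (r=-0.42, power 0.95 at N=55). Also, -0.796 is an MCA figure from a pilot with five subjects, while total CBF is basilar plus both internal carotids. This stands: the ROI column shows what the rule permits and does not forecast the result. The artery column follows the pattern expected at rest. It supposes that the follow-ups include resting artery values, although the sentence names only changes.

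**Aim 3 has a partial safeguard.** Joint significance also needs the HOMA-IR-to-perfusion path. If domain-level tests use the same method, cross-opening matters mainly when only the perfusion-to-cognition path is null.

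**Stronger readings that the documents do not support.**
- A reader might infer that the plan's whole Type I error argument fails. It does not: Aim 1 has a single gate on its own family, and the total tests do not depend on these sentences.
- A reader might also blame the word 'either' for the chance that some total is falsely significant, 1-0.95² = 0.0975 for two independent totals or 1-0.95⁴ = 0.185 for four. Those figures come from testing several totals at 0.05 each, and own-family gates leave them unchanged.

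**Conclusion.** The point holds for cross-opened follow-ups in Aims 2 and 3, on the literal text. For those tests the Section 8 statement of no increased Type I error is not true. In a fully null family, the chance of at least one false positive is 0.46 down to 0.12 for 12 ROIs when the macro total is almost surely significant. It is about 0.33 down to 0.10 for 11 arteries when the resting micro total opens the gate. An own-composite gate gives about 0.05.

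The ranges rest on an assumed within-family correlation of 0 to 0.9, on one-sided 0.05 follow-ups, and on counting only the 12 ROIs given as examples. The existence of the problem in Aim 3 follows from the wording; its size is not known.

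Severity is moderate. The exposure is limited to secondary follow-up analyses; the total tests, N=55 and the stated powers do not change.

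**What to change.** - In 8.3.3, state that ROI tests follow only a significant CVC_MICRO total, and artery tests only a significant CVC_MACRO total, in the same state (rest or change during OGTT).
- In 8.4, state that domain-level mediation is examined only for the mediator and state whose own joint test was significant.
- Label every other follow-up exploratory.

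The cost is one sentence in each section plus the label, settled before analysis, with no new data or subjects. The downside is fewer confirmatory follow-up tests. Own-family gates also have a limit that the text should admit: they protect only when the whole family is null. They do not give strong control when some ROIs or arteries are truly related to HOMA-IR. If that is wanted, an adjustment within the family, such as Holm, would have to be added.
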